8. SELECTION AND WITHDRAWAL OF SUBJECTS

Subjects must meet all of the inclusion criteria to be included in this study and any subjects meeting any of the exclusion criteria will be excluded from this study.

8.1. Study Population

8.1.1. Inclusion Criteria

- 1. Men and women of 18 years of age and older
- 2. Voluntary agreement to provide written informed consent and the willingness and ability to comply with all aspects of the protocol
- 3. Eastern Cooperative Oncology Group (ECOG) score of 0, 1, or 2 (Appendix 1)
- 4. Life expectancy (in the opinion of the Investigator) of ≥ 3 months before enrollment
- 5. Have histologically confirmed FL, Grade 1 to 3a. Subjects may have R/Rdisease following at least 2 standard prior systemic treatment regimens where at least 1 anti-CD20-based regimen was used
- 6. Treatment recommended in accordance with the Groupe d'Etude des Lymphomes Folliculaires (GELF) criteria due to the presence of at least one of the following:
 - a. Any nodal or extranodal tumor mass >7 cm diameter
 - b. Involvement of at least 3 nodal sites, each with diameter >3 cm
 - c. Presence of any systemic or B symptoms
 - d. Splenic enlargement with inferior margin below the umbilical line
 - e. Compression syndrome (ureteral, orbital, gastrointestinal)
 - f. Pleural or peritoneal serous effusion (irrespective of cell content)
 - g. Leukemic phase (>5.0 x 10⁹/L circulating malignant cells)
 - h. Cytopenias (granulocyte count $\leq 1.0 \times 10^9/L$ and/or platelets $\leq 100 \times 10^9/L$)
- 7. Meet the following laboratory parameters:
 - a. Absolute neutrophil count (ANC) \geq 750 cells/ μ L (0.75 x 10⁹/L), or \geq 500 cells/ μ L (0.50 x 10⁹/L) in subjects with documented bone marrow involvement
 - b. Platelet count $\geq 50,\!000$ cells/µL (50 x 109/L), or $\geq 30,\!000$ cells/µL (30 x 109/L) in subjects with documented bone marrow involvement, and without transfusion dependence
 - c. Hemoglobin $\geq 8 \text{ g/dL}$
 - d. Serum alanine aminotransferase (AST) and aspartate aminotransferase (ALT) \leq 3.0 x ULN, unless related to disease involvement
 - e. Total bilirubin ≤ 1.5 x ULN, unless due to disease involvement, Gilbert's syndrome, or hemolytic anemia

- f. Estimated creatinine clearance (ie, estimated glomerular filtration rate [eGFR] using Cockcroft-Gault [Appendix 4]) ≥ 40 mL/min
- 8. At least one bi-dimensionally measurable nodal lesion > 1.5 cm in its longest diameter by computed tomography (CT) scan or magnetic resonance imaging (MRI) excluding lesions that meet the following criteria:
 - a. Previously irradiated lesions should not be counted as target lesions
 - b. Lesions that are intended to be used to collect tissue samples for biopsy should not be counted as target lesions
 - c. Bone lesions should not be counted as target lesions
- 9. Any clinically significant toxicity related to a prior anticancer treatment (ie, chemotherapy, immunotherapy, and/or radiotherapy), except for alopecia, either resolved to ≤ Grade 1 per National Cancer Institute (NCI) Common Terminology Criteria for Adverse Events (CTCAE) Version 5.0 or is clinically stable and no longer clinically significant
- 10. Negative serologic or polymerase chain reaction (PCR) test results for acute or chronic hepatitis B virus (HBV) infection (Appendix 7)
 - Note: Patients whose HBV infection status could not be determined by serologic test results must be negative for HBV-DNA by PCR to be eligible for study participation. Patients seropositive for HBV with undetectable HBV-DNA by PCR are permitted with appropriate antiviral prophylaxis.
- 11. Negative test results for hepatitis C virus (HCV) (Appendix 8) and human immunodeficiency virus (HIV)
 - Note: Patients who are positive for HCV antibody must be negative for HCV-RNA by PCR to be eligible for study participation.
- 12. Females of childbearing potential (FCBP) must have a negative serum pregnancy test (beta-human chorionic gonadotropin [β-hCG] test with a minimum sensitivity of 25 mIU/mL or equivalent units of β-hCG) at screening and within 24 hours prior to the first dose of study drug. All females will be considered to be of childbearing potential unless they are naturally postmenopausal (at least 12 months consecutively amenorrhoeic [amenorrhea following cancer therapy does not rule out childbearing potential] and without other known or suspected cause) or have been sterilized surgically (ie, total hysterectomy and/or bilateral oophorectomy, with surgery completed at least 28 days prior to the first dose of study drug).
- 13. FCBP must either practice complete abstinence or agree to use a highly effective method of contraception beginning at least 28 days prior to the first dose of study drug, during study treatment (including during dose interruptions), for 6 months after tazemetostat discontinuation, and for 12 months after rituximab discontinuation. If the contraception methods provided in Section 9.3 are not appropriate for the FCBP, she must be referred to a qualified contraception provider to determine the medically effective contraception method appropriate for the subject. Examples of highly effective methods of contraception (result in a failure rate of <1% per year when used consistently and correctly) may be found in Section 9.3 . Female subjects must also refrain from

Protocol EZH-1401 Amendment 2.0 21 October 2021

breastfeeding or donating oocytes during study treatment and for 12 months following the last dose of rituximab.

14. Male subjects must have had a successful vasectomy (with medically confirmed azoospermia) OR must either practice complete abstinence or agree to use a latex or synthetic condom during sexual contact with a FCBP from the first dose of study drug, during study treatment (including during dose interruptions), and for 3 months after study drug discontinuation.

NOTE: Male subjects must not donate sperm from the first dose of study drug, during study treatment (including during dose interruptions), and for 3 months after study drug discontinuation.

8.1.2. Exclusion Criteria

- 1. Prior exposure to tazemetostat or other inhibitor(s) of EZH2
- 2. Grade 3b, mixed histology, or transformed FL
- 3. Treatment with any of the following anticancer therapies within the indicated timeframe of a specific treatment prior to first dose of study drug:
 - a. Cytotoxic chemotherapy within 21 days
 - b. Noncytotoxic chemotherapy (e.g., small molecule inhibitor) within 14 days
 - c. Nitrosoureas within 6 weeks
 - d. Prior immunotherapy within 4 weeks
 - e. Radiotherapy within 6 weeks from prior radioisotope therapy; within 12 weeks from 50% pelvic or total body irradiation
 - f. Any investigational treatment within 4 weeks or at least 5 half-lives, whichever is shorter
- 4. History of solid organ transplant
- 5. Major surgery within 4 weeks of the start of study treatment
- 6. Thrombocytopenia, neutropenia, or anemia of Grade > 3 (per CTCAE v5.0 criteria) or any prior history of myeloid malignancies, including MDS/AML or MPN
- 7. Prior history of T-LBL/T-ALL
- 8. Unwillingness to exclude grapefruit juice-containing products, Seville oranges, and grapefruits from the diet and/ or consumed within 1 week of the first dose of study drug
- 9. Subjects taking medications that are known strong cytochrome P450 (CYP)3A inhibitors and strong or moderate CYP3A inducers (including St. John's wort) (See Section 9.2.5 and https://drug-interactions-table-substrates-inhibitors-and-inducers; https://drug-interactions.medicine.iu.edu/MainTable.aspx)
- 10. Any uncontrolled illness including, but not limited to, significant active infection requiring systemic (IV) therapy, hypertension, angina, arrhythmias, pulmonary disease, autoimmune dysfunction, immune thrombocytopenia, or autoimmune hemolytic anemia

- 11. History of clinically significant cardiovascular abnormalities such as congestive heart failure (New York Heart Association classification > II [Appendix 6]), myocardial infarction or stroke within 6 months of first dose of study drug
- 12. History of clinically significant gastrointestinal (GI) conditions, particularly:
 - a. Known GI condition that would interfere with swallowing or the oral absorption or tolerance of study drug
 - b. Pre-existing malabsorption syndrome or other clinical situation that would affect oral absorption
- 13. Other diagnosis of cancer that is likely to require treatment in the next 2 years, with the exception of the following:
 - a. Curatively treated basal cell carcinoma or squamous cell carcinoma of the skin
 - b. Curatively treated carcinoma in situ of the cervix
 - c. Hormonal therapy for prostate cancer
- 14. Females who are pregnant or lactating/breastfeeding
- 15. Received a live virus vaccination within 28 days of first dose of rituximab
- 16. Concurrent participation in a separate investigational therapeutic study
- 17. Psychiatric illness/social situations that would interfere with study compliance

8.2. Subject Withdrawal Criteria

Subjects will be treated for 6 cycles of combination therapy followed by 18 cycles of tazemetostat monotherapy across the trial or until disease progression or unacceptable toxicity or withdrawal of consent.

A subject removed from the study for any reason may not be replaced.

8.2.1. Withdrawal of Subjects from Study Treatment/Procedures

Subjects have the right to withdraw from the study at any time and for any reason without penalty or prejudice to future medical care by the physician or institution. The Investigator is also free to terminate a subject's study drug treatment at any time if the subject's clinical condition warrants it. Subject data up to withdrawal of consent will be included in the analysis of the study, and where permitted, publicly available data can be included after withdrawal of consent (eg, death records).

Subjects (or legally authorized representatives) can decline to continue receiving any study treatment and/or other protocol-required procedures at any time during the study but can continue participation in the study (eg, for follow-up information). If this occurs, the Investigator is to discuss with the subject (or legally authorized representatives) appropriate processes for discontinuation and the options for procedures that may continue such as collection of data, including endpoints and AEs. The Investigator must document the agreement in the procedures that the subject will continue with and the level of follow-up that is agreed to by the subject (eg, in person, by telephone/mail, through family/friends, in correspondence/communication with other physicians, from review of the medical records.) If a subject voluntarily withdraws from the study, the investigator should attempt to contact the subject to determine the reason(s).

Protocol EZH-1401 Amendment 2.0 21 October 2021

The primary reasons for discontinuation or withdrawal of a subject from protocol-required treatment or procedures must be determined using the following categories:

- Confirmed disease progression by Investigator
- Confirmed disease progression by independent radiologic review
- Death
- Subject request to end study treatment and/or procedures
- Withdrawal of consent
- AE
- Pregnancy
- Noncompliance with study drug
- Lost to follow-up
- Physician decision
- Termination of study by Sponsor
- Any other reason that, in the opinion of the Investigator, would justify removing the subject from the study drug, based on the interest of the subject

8.2.2. Subsequent Therapy After Discontinuation of Study Treatment

Once a subject has permanently discontinued study treatment, every effort should be made to have the subject complete the End-of-Treatment and Survival Follow-up visits prior to initiating any subsequent anticancer therapy (approved or investigational). Post-study anticancer therapy will not be provided as part of this study. The subject may receive subsequent anticancer therapy at the discretion of the treating physician. The subsequent anticancer therapy should be documented on the electronic case report form (eCRF). The subject will continue to be monitored until disease progression.

9. TREATMENT OF SUBJECTS

All subjects will receive tazemetostat in combination with rituximab as described in following sections.

9.1. Description of Study Drug

In June 2020, the US FDA granted accelerated approval of TAZVERIK (tazemetostat) in the US for the treatment of adult patients with R/R FL whose tumors are positive for an EZH2 mutation as detected by an FDA-approved test and who have received at least 2 prior systemic therapies, and for the treatment of adult patients with R/R FL who have no satisfactory alternative treatment options.

Earlier, in January 2020, the US FDA granted accelerated approval to TAZVERIK for adults and pediatric patients aged 16 years and older with metastatic or locally advanced epithelioid sarcoma not eligible for complete resection.

Tazemetostat (EPZ-6438) is an Epizyme IP and is defined as an Investigational Medicinal Product (IMP) under the European Union Clinical Trials Directive (EU CT Dir). The contents of the package label will be in accordance with all applicable regulatory requirements. The expiry date will be printed on the label.

Tazemetostat is available as tablets in 200 mg strength and supplied in white HDPE bottles. Additional details on tazemetostat can be found in Table 3 and Section 10.1.

Table 3: Chemical Name, Structural Formula of Tazemetostat

Test drug code:	EPZ-6438
International non-proprietary name:	Tazemetostat
Chemical name:	[1,1'-Biphenyl]-3-carboxamide, N -[(1,2-dihydro-4,6-dimethyl-2-oxo-3-pyridinyl)methyl]-5-[ethyl(tetrahydro-2 H -pyran-4-yl)amino]-4-methyl-4'-(4-morpholinylmethyl)-, hydrobromide (1:1)
Molecular formula:	C ₃₄ H ₄₄ N ₄ O ₄ ·HBr (Hydrobromide salt)
	C ₃₄ H ₄₄ N ₄ O ₄ (Free base)
Molecular weight:	653.66 (Hydrobromide salt) 572.75 (Free base)
Structural formula:	• HBr

9.2. Concomitant Medication

9.2.1. Prior and Concomitant Medications

Prior and concomitant medications include all prescription and nonprescription medications, vitamins, herbals (including medical marijuana), and transfusions.

All prior medications (including over-the-counter medications) administered 30 days before the first dose of study drug will be recorded. Any concomitant therapy administered to the subject during the course of the study (starting at the date of first dose of informed consent) until 30 days after the final dose of study drug or until initiation of subsequent anticancer therapy will be recorded. Additionally, all diagnostic, therapeutic, or surgical procedures relating to malignancy should be recorded.

9.2.2. Permitted Concomitant Medications

Any medication that is considered necessary for the subject's health and that is not expected to interfere with the evaluation of or interact with tazemetostat may be continued during the study.

Subjects enrolled may receive prophylaxis treatment for *Pneumocystis jirovecii* at the discretion of the Investigator.

Subjects may receive prednisone (or equivalent corticosteroid) for systemic or local symptom control prior to and while on study. However, starting at Cycle 1 Day 1, subjects may receive no more than 10 mg of prednisone (or equivalent corticosteroid) daily when used for treatment of lymphoma related symptoms, with the intent to taper by the end of Cycle 1.

Treatment of complications, AEs or therapy to ameliorate symptoms (including blood products, blood transfusions, fluid transfusions, antibiotics, antidiarrheal drugs, etc.) may be given at the discretion of the Investigator, unless it is expected to interfere with the evaluation of (or to interact with) tazemetostat. The Investigator will record any AE on the AE eCRF for which the concomitant medication/therapy was administered.

Over-the-counter medications, nutritional supplements, vitamins, and herbal preparations are permitted under physician recommendation only. Aspirin, nonsteroidal anti-inflammatory drugs, and low-molecular-weight heparin or prophylactic doses of heparin are permissible but should be used with caution. Granulocyte colony-stimulating factor (G-CSF), or equivalent, may be used in accordance with American Society of Clinical Oncology (ASCO) (Smith, 2015), institutional, or national guidelines. Erythropoietin may be used according to ASCO, institutional, or national guidelines.

9.2.3. Premedication for Rituximab

Premedication with an antihistamine and acetaminophen is required for all rituximab administration, including both IV infusion and subcutaneous injection. Additional premedication for subjects receiving rituximab may be given according to institutional practice and current product prescribing information.

9.2.4. Permitted Radiation Therapy

Palliative radiotherapy may be given for the control of pain or for other reasons (ie, bronchial obstruction, ulcerating skin lesions, etc) with no curative intent. The irradiated area should be as small as possible and should never involve more than 10% of the bone marrow in any given 4-week period for distribution of active bone marrow. The irradiated area cannot be used as a parameter for response assessment. Treatment with tazemetostat should be delayed in subjects receiving palliative radiotherapy after discussion with the Medical Monitor. In addition, other palliative procedures intended for symptom control and concurrent dose interruptions may be permitted after discussion with the Medical Monitor.

9.2.5. Prohibited Concomitant Therapies and Drugs

Subjects must not receive other antitumor therapies while on study. Prohibited antitumor medications during this study are any other investigational or unapproved drugs, and other anticancer therapies unless otherwise stated. If a subject receives any prohibited antitumor medications, this will be judged as evidence of disease progression, and study drug will be discontinued. In this case, the subject should complete all off-treatment assessments and be followed for survival in the Survival Follow-up period.

Known strong CYP3A inhibitors and strong or moderate CYP3A inducers (including St. John's wort) are prohibited within 14 days prior to the first dose of study drug (tazemetostat) and for the duration of the study. Coadministration of tazemetostat with a strong or moderate CYP3A inhibitor increases tazemetostat plasma concentrations, which may increase the frequency or severity of adverse reactions.

Coadministration of tazemetostat with a strong or moderate CYP3A inducer may decrease tazemetostat plasma concentrations, which may decrease the efficacy of tazemetostat. Because there is a potential for interaction of tazemetostat with other concomitantly administered drugs through the cytochrome P450 system, all over-the-counter medications, and alternative therapies, in addition to prescribed medications, must be recorded in the eCRF. The Investigator should be alerted if the subject is taking any agent known to affect or with the potential to affect selected CYP450 isoenzymes.

Medications that are strong CYP3A inhibitors and strong or moderate CYP3A inducers include, but are not limited to, those listed in Table 4 (refer to product information and the source websites in Table 4 for the most up-to-date information).

Table 4: Examples of Strong and Moderate Clinical CYP3A Inhibitors and Inducers and Clinical CYP3A Sensitive Substrates for P450-Mediated Metabolisms

Strong Inhibitors	Moderate Inhibitors	Strong Inducers	Moderate Inducers	Sensitive Substrates
boceprevir	aprepitant	apalutamide	bosentan	alfentanil
clarithromycin ^a	ciprofloxacin	carbamazepine	efavirenz	avanafil
cobicistata	conivaptan ^d	enzalutamide ^f	etravirine	budesonide
danoprevir and	crizotinib	mitotane	phenobarbital	buspirone
ritonavir ^b	cyclosporine	phenytoin	primidone	conivaptan
elvitegravir and	diltiazeme	rifampin		darifenacin
ritonavir ^b	dronedaronea	St. John's wortg		darunavir ^h
grapefruit juice ^c	erythromycin			dasatinib

Strong Inhibitors	Moderate Inhibitors	Strong Inducers	Moderate Inducers	Sensitive Substrates
idelalisib	fluconazole			dronedarone
indinavir and	fluvoxamine			ebastine
ritonavir ^b	imatinib			eletriptan
itraconazole ^a	tofisopam			eplerenone
ketoconazole	verapamil ^a			everolimus
lopinavir and				felodipine
ritonavir ^{a,b}				ibrutinib
nefazodone				indinavir ^h
nelfinavira				lomitapide
paritaprevir and				lovastatin ⁱ
ritonavir and				lurasidone
(ombitasvir and/or				maraviroc
dasabuvir) ^b				midazolam
posaconazole				naloxegol
ritonavir ^{a,b}				nisoldipine
saquinavir and				quetiapine
ritonavir ^{a,b}				saquinavir ^h
telaprevir ^a				sildenafil
telithromycin				simvastatin ⁱ
tipranavir and				sirolimus
ritonavir ^{a,b}				tacrolimus
troleandomycin				ticagrelor
voriconazole				tipranavir ^h
				tolvaptan
				triazolam
				vardenafil

Source: US Food and Drug Administration. Drug Development and Drug Interactions: Table of Substrates, Inhibitors, and Inducers. March 2020; https://www.fda.gov/drugs/drug-interactions-labeling/drug-development-and-drug-interactions-table-substrates-inhibitors-and-inducers

Flockhart DA. Drug Interactions: Cytochrome P450 Drug Interaction Table. Indiana University School of Medicine. 2020; https://drug-interactions.medicine.iu.edu/MainTable.aspx

Abbreviations: AUC = area under the concentration-time curve; CYP = cytochrome p450; OATP1B1 = organic anion transporting polypeptide 1B1; P-gp = P-glycoprotein.

- ^a Inhibitor of P-gp (defined as those increasing AUC of digoxin to ≥1.25-fold).
- ^b Ritonavir is usually given in combination with other anti-HIV or anti-HCV drugs in clinical practice. Caution should be used when extrapolating the observed effect of ritonavir alone to the effect of combination regimens on CYP3A activities.
- ^c The effect of grapefruit juice varies widely among brands and is concentration-, dose-, and preparation-dependent. Studies have shown that it can be classified as a "strong CYP3A inhibitor" when a certain preparation was used (eg, high dose, double strength) or as a "moderate CYP3A inhibitor" when another preparation was used (eg, low dose, single strength).
- ^d The classification is based on studies conducted with intravenously administered conivaptan.
- ^e Diltiazem increased AUC of certain sensitive CYP3A substrates (eg, buspirone) more than 5-fold.
- ^f Except as prescribed in this study.
- ^g The effect of St. John's wort varies widely and is preparation-dependent.
- h Usually administered to subjects in combination with ritonavir, a strong CYP3A inhibitor.
- ⁱ Acid form is an OATP1B1 substrate.

Note: These lists of example medications are not exhaustive; refer to specific product information and the source websites in this table for current information.

Use of live vaccines is prohibited 4 weeks (28 days) prior to initiation of study treatment and during study treatment with rituximab.

9.2.6. Concomitant Medications to be used with Caution

The following medications are to be used with caution:

- CYP3A sensitive substrates
- Moderate CYP3A inhibitors. If coadministration with a moderate CYP3A inhibitor cannot be avoided, reduce the dose of tazemetostat as shown in Table 5. After discontinuation of the moderate CYP3A inhibitor for 3 elimination half-lives, resume the tazemetostat dose that was being taken prior to initiating the inhibitor.

Table 5: Tazemetostat Dose Reduction for Coadministration with Moderate CYP3A Inhibitors

Current Dosage	Adjusted Dosage
800 mg twice daily	400 mg twice daily
600 mg twice daily	400 mg for first dose and 200 mg for second dose
400 mg twice daily	200 mg twice daily

Examples of CYP3A sensitive substrates and moderate CYP3A inhibitors include, but are not limited to, those listed in Table 4. This list of medications is not exhaustive; refer to product information and the source websites in Table 4 for the most up-to-date information.

Refer to product information for rituximab for guidance regarding concomitant medications use and cautions related to interaction with other medications.

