The most common TEAEs leading to tazemetostat dose reduction in the adult population were thrombocytopenia, neutropenia and diarrhea, each reported in <1% of adult subjects.

In addition, as described in Section 12.2.2, AESIs identified for the tazemetostat development program include: T-cell lymphoblastic lymphoma (T-LBL)/ T-cell acute lymphoblastic leukemia (T-ALL), myelodysplastic syndrome (MDS), AML (acute myeloid leukemia), and other myeloid malignancies like myeloproliferative neoplasm (MPN). Epizyme considers the risk for T-LBL/T-ALL in tazemetostat clinical trials to be largely concentrated in pediatric patients. One event of T-LBL has occurred in pediatric subjects (n=109). The risk of T-LBL/T-ALL in adults is not known; however, the incidence of treatment-related T-LBL/T-ALL in adults is expected to be uncommon. As of 12 April 2021, over 958 subjects (adults and pediatrics) have been treated with tazemetostat as monotherapy and in combination other anti-neoplastic therapies with no other reported cases of T-LBL/T-ALL.

As of 12 April 2021, 7 myeloid malignancies have been reported in an estimated cumulative exposure of 1521 patients from both clinical and post-marketing sources. All 7 events were reported in adult clinical trial subjects. The risk of myeloid neoplasms as a result of EZH2 inhibition is considered uncertain based on available literature and Epizyme clinical data. Measures are in place to exclude potential subjects who may be predisposed to developing a myeloid neoplasia from participation in clinical studies and for early identification and monitoring of subjects who may be developing a myeloid neoplasia.

A single event of B-cell acute lymphoblastic leukemia (B-ALL) was reported in an adult subject with predisposing factors and is considered under evaluation. Refer to Section 12.2.4.2.1 for further details.

Measures are in place to exclude potential subjects who may be predisposed to developing a myeloid/lymphoid neoplasia from participation in clinical studies and for early identification and monitoring of subjects who may be developing a myeloid/lymphoid neoplasia.

Further details of study designs, tazemetostat exposure, and TEAEs regardless of causality are outlined in the current IB.

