7.4. Dose Adjustment Criteria

7.4.1. Dose Adjustment for Tazemetostat

Tazemetostat dose reductions and interruptions will be allowed; however, an interruption in the administration of tazemetostat for more than 14 days must be discussed with the Medical Monitor before treatment can be resumed.

Toxicity will be managed by concomitant medication (as appropriate), treatment interruption, dose reduction, and treatment discontinuation, or a combination of these. During treatment with tazemetostat, dose interruption and reduction for subjects who experience tazemetostat-**related** toxicity will be in accordance with the Dose Modifications instructions in Table 1.

For subjects who require dose interruption due to tazemetostat-related toxicity, the treatment may restart once the toxicity has been resolved to Grade ≤ 1 or baseline, unless otherwise noted, according to the Dose Modifications instructions in Table 1. No tazemetostat dose re-escalation is permitted.

For continuation of treatment for Cycle 2 and beyond, subjects must meet the following retreatment criteria:

- Platelet count must be $> 50 \times 10^9/L$
- Absolute neutrophil count (ANC) must be $\geq 0.75 \times 10^9 / L$, and
- Any Grade 3 or higher toxicity must have resolved to ≤Grade 1 or baseline, unless otherwise noted

Table 1: Dose Modifications for Tazemetostat Treatment-Related Toxicities

Tazemetostat-Related Toxicity ^a	During Therapy	Approximate Dose Adjustmentb			
	Grade 1				
All occurrences	All occurrences Continue tazemetostat				
	Grade 2 ^{c,d}				
1st occurrence		Maintain dose level			
2 nd occurrence (same or new toxicity)	Interrupt tazemetostat until	Restart at 600 mg BID			
3 rd occurrence (same or new toxicity)	resolved to Grade ≤ 1 or baseline ^b	Restart at 400 mg BID			
4 th occurrence (same or new toxicity)		Discuss with Medical Monitor			
Grade 3 ^c (Not Including Neutropenia and Thrombocytopenia)					
1 st occurrence		Restart at 600 mg BID			

Tazemetostat-Related Toxicity ^a	During Therapy	Approximate Dose Adjustmentb						
2 nd occurrence (same or new toxicity)	$\begin{array}{c} \text{Interrupt tazemetostat until} \\ \text{resolved to Grade} \leq 1 \text{ or baseline}^b \end{array}$	Restart at 400 mg BID						
3rd occurrence (same or new toxicity)	Discontinue tazemetostat	Not applicable						
Grad	Grade 3 Neutropenia (ANC: < 1.0 – 0.5 × 10 ⁹ /L) ^e							
ANC $\ge 0.75 \times 10^9 / L$	Continue tazemetostat	Maintain dose level						

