5.2. Final Analysis

The study is terminated early with 5 treated patients and the planned analyses specified in the protocol will not be performed. Only selected analyses will be provided to support synoptic CSR.

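### Section 9.2.6 returns subjects to their pre-inhibitor tazemetostat dose with no exception for a toxicity reduction made in between, which conflicts with the no-re-escalation rule in Section 7.4.1

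*Protocol*

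**What the plan says.** Three parts of the protocol bear on this.

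- **Section 9.2.6 and Table 5 (moderate CYP3A inhibitors).** If a moderate inhibitor cannot be avoided, tazemetostat is reduced: 800 mg BID becomes 400 mg BID, 600 mg BID becomes "400 mg for first dose and 200 mg for second dose", and 400 mg BID becomes 200 mg BID. The way back is: "After discontinuation of the moderate CYP3A inhibitor for 3 elimination half-lives", "resume the tazemetostat dose that was being taken prior to initiating the inhibitor". The section has no exception for toxicity, no reference to 7.4.1 or Table 1, and no Medical Monitor step.
- **Section 7.4.1 and Table 1 (toxicity).** Related toxicity leads to interruption and then restart at a stated level. For a first related Grade 3 event (other than neutropenia or thrombocytopenia) the entry is "Restart at 600 mg BID"; for a second it is 400 mg BID. The paragraph on restarting after a toxicity interruption ends: "No tazemetostat dose re-escalation is permitted". It does not mention inhibitor adjustments. Apart from certain Table 1 rows, the Medical Monitor must be consulted only when an interruption exceeds 14 days.
- **Section 9.2.5.** Coadministration with a strong or moderate inhibitor "increases tazemetostat plasma concentrations, which may increase the frequency or severity of adverse reactions".

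The SAP does not deal with dose adjustment.

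**The concern.** The dose taken before the inhibitor is the right one to resume only if nothing else has lowered the subject's level in the meantime. Section 9.2.6 does not say so. A subject who started the inhibitor at 800 mg BID and had a related toxicity that moved them to the 600 or 400 mg BID level would, on the wording of 9.2.6, go back to 800 mg BID when the inhibitor stops. That undoes a safety reduction and gives a dose that 7.4.1 forbids.

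What is at stake is the safety of an individual subject and the clarity of the instruction to sites. No planned analysis is affected.

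**Working it through.** The protocol states no figure for this situation, so the check sets the two instructions side by side and compares daily doses.

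**Inputs.** Dose levels of 800, 600 and 400 mg BID (Sections 7.3 and 7.4.1, Table 1); inhibitor conversions (Section 9.2.6, Table 5); the resume rule (9.2.6); the re-escalation rule (7.4.1).

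**Step 1. Table 5 on its own.** Daily dose before and on the inhibitor:

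- 800 level: 1,600 to 400 + 400 = 800 mg/day
- 600 level: 1,200 to 400 + 200 = 600 mg/day
- 400 level: 800 to 200 + 200 = 400 mg/day

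Each is a 50% cut. With no toxicity in between, the return simply reverses it. Table 5 is internally consistent.

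**Step 2. One subject followed through.**

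1. Starts at 800 mg BID, 1,600 mg/day.
2. Begins a moderate inhibitor; Table 5 gives 400 mg BID.
3. Has a first related Grade 3 event; Table 1 sets the level at 600 mg BID, 1,200 mg/day.
4. The inhibitor stops. Section 9.2.6 gives the pre-inhibitor dose, 800 mg BID or 1,600 mg/day. Section 7.4.1 does not allow a rise above the 600 mg BID level.

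One toxicity event is enough to produce the conflict. If the reduction came before the inhibitor, the pre-inhibitor dose is already the reduced one and there is no conflict.

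**Step 3. All cases.** Let L0 be the dose before the inhibitor and L1 the Table 1 level assigned while on it. Table 1 prints no level below 400 mg BID, so L1 < L0 can occur in three ways. The excess of the literal 9.2.6 dose over the toxicity-assigned level is 2·L0 / (2·L1) − 1.

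| L0 (mg BID) | L1 (mg BID) | 9.2.6 literal (mg/day) | Toxicity level (mg/day) | Excess |
|---|---|---|---|---|
| 800 | 600 | 1,600 | 1,200 | 1,600/1,200 − 1 = 33% |
| 800 | 400 | 1,600 | 800 | 1,600/800 − 1 = 100% |
| 600 | 400 | 1,200 | 800 | 1,200/800 − 1 = 50% |

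**Step 4. The same cases under a lower-of rule, min(L0, L1).** The resumed doses are 600, 400 and 400 mg BID, that is 1,200, 800 and 800 mg/day. None of the three exceeds the toxicity-assigned level. With no toxicity reduction L1 = L0, and the ordinary return is unchanged.

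**The case against.** The strongest answer is one of scope. The ban on re-escalation closes a paragraph about interruption for related toxicity, so it governs Table 1 reductions; 9.2.6 governs a planned interaction adjustment. Read that way, the Table 5 halving is reversed when the inhibitor stops, a Table 1 reduction never is, and both sections work. This is sound as far as it goes, and it is the better reading. A reader might infer that 9.2.6 can operate only as an unlimited exception to 7.4.1, because every return from Table 5 doubles the daily dose. The placement of the ban does not support that: an ordinary return without toxicity need not breach it.

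What remains is that the site must work this out for itself. The text specific to stopping an inhibitor is explicit, has no exception and does not point to 7.4.1. On its wording it gives a dose that 7.4.1 bars.

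Three other inferences are tempting and should not be drawn.

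- *That Table 1's absolute restart doses are faulty in the same way.* This needs occurrence counts that run separately for each block, which is inferred from layout and not stated. It also needs at least three toxicity events, and the ban beside the table then still fixes the dose.
- *That the increase should be measured from the dose taken on the inhibitor.* This assumes that a Table 1 restart level is converted through Table 5 while the inhibitor continues. That is sensible, but Table 1 does not say it.
- *That the warning in 9.2.5 makes the case common.* The warning concerns raised concentrations on coadministration, and Table 5 halves the dose in response. The protocol does not say that toxicity is increased after that halving, and 9.2.6 reserves moderate inhibitors for use that cannot be avoided.

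**Conclusion.** The point holds as a conflict between two dosing instructions in one uncommon situation: a toxicity reduction made while a moderate inhibitor is in use, followed by stopping the inhibitor. Followed literally, 9.2.6 exceeds the toxicity-assigned level by 33%, 100% or 50%. These figures assume that the site applies 9.2.6 as written and does not read 7.4.1 across to it; a site that does read it across would give the lower dose.

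Frequency cannot be estimated from the documents. Section 5.2.2 gives the most common causes of dose reduction in adults as three events, "each reported in <1% of adult subjects". A reader might add these to get an upper bound, but the sum leaves out every other cause. The documents also give no reduction rate for the rituximab combination or during inhibitor use, and no share of subjects on a moderate inhibitor that later stops.

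Response rate, alpha, power and the futility rule are unaffected. SAP Section 5.2 records: "The study is terminated early with 5 treated patients". This is a minor correction to a safety instruction, and its practical value now lies mainly in any reuse of this dosing text.

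**What to change.** In Section 9.2.6, replace the resume instruction with: *resume the lower of the dose taken before the inhibitor and the current toxicity-assigned level under Table 1 (before Table 5 conversion); see Section 7.4.1.*

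The words in brackets make clear that the comparison is with the Table 1 level itself and not with the halved dose taken on the inhibitor. The cost is one sentence and a cross-reference, with no new procedure, visit or data item.
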